1. STUDY OBJECTIVES

1.1 Primary Objective

To determine the peripheral blood minimum residual disease (MRD)-negative complete response (CR) rate of the combination of acalabrutinib + lenalidomide + rituximab (ALR) at the conclusion of 12 cycles of induction therapy.

1.2 Secondary Objectives

- Safety and tolerability of the ALR combination
- Best overall response rate
- Complete response rate
- Progression free survival (time frame up to 2 years)
- Overall survival (time frame up to 2 years)
- Safety and feasibility of the ALO cohort

1.3 Exploratory Objectives

- To evaluate peripheral blood MRD status during maintenance treatment.
- To estimate the response rate to the next subsequent therapy.
- To estimate the prevalence of adverse events over time.
- To estimate the quality of life of participants during the first 24 months of therapy.
- To correlate NGS mutational profile with response to treatment of the following genes: ATM, CCND1, TP53, KMT2D, NOTCH1, NOTCH2, WHSC1 and BIRC3.
- To evaluate the change in immune cells in peripheral blood, including T and NK cell subpopulations and the MDSC subset in response to treatment.
- To evaluate the cytokine profile (blood) in response to treatment.
- To analyze kinetics of changes of peripheral blood cell-free tumor DNA (cfDNA) in the plasma following study regimen and to evaluate cfDNA in the context of response status.
- To evaluate the immune metabolic profile (blood) pre-treatment, following ALR, and at time of progression.

2. BACKGROUND

2.1 Mantle Cell Lymphoma

Mantle cell lymphoma (MCL) is an incurable lymphoma with a median survival of 5-7 years. Standard front-line treatment usually includes chemoimmunotherapy and often involves aggressive approaches, yet most patients continue to relapse despite intensive therapy. The major therapeutic goals in patients with MCL are to prolong survival and improve quality of life. The unmet needs in MCL management in the frontline setting are to develop approaches that can be targeted to the appropriate patients based on disease biology, are well tolerated and accessible by

all patients, and can be administered in the outpatient community¹.

Over the past decade, four non-chemotherapy options, namely bortezomib, lenalidomide, ibrutinib, and most recently acalabrutinib, have been approved by the United States Food and Drug Administration for treatment of MCL²⁻⁵. Continuous therapy with BTK inhibitors in particular have shown impressive clinical activity with generally favorable toxicity profile in relapse/refractory setting. The introduction of novel agents corresponds with better outcomes in population studies, suggesting that the availability of new options that can be used sequentially may be extending survival. Furthermore, emerging data with novel agents and combinations is poised to challenge the conventional chemotherapy-based treatment paradigm in frontline setting, making effective and less toxic “chemo-free” treatment accessible to most MCL patients a tangible reality.

Recently published data from Weill Cornell Medicine (WCM) have shown that the combination of lenalidomide plus rituximab administered until progression is active and well tolerated as front-line therapy in patients with MCL with a complete response (CR) rate of 61%, a 2-year progression-free survival (PFS) of 85% and a 4-year PFS of 70%, demonstrating the feasibility of administering novel agents as effective induction and chronic maintenance therapy in the outpatient setting⁶. MRD status was sampled during long-term follow-up, and 6 of 7 patients with available samples achieved MRD negativity⁷, providing the first proof-of-concept evidence that lenalidomide-based novel agent/combination have the potential to achieve MRD-negative remission. The apparent activity of the regimen warrants further evaluation, but attempts at improving the efficacy and tolerability as well as efforts to better define the patient subsets that might benefit most are also needed.

2.2 Application of Chemotherapy-free Novel Agents in MCL

Both lenalidomide-based and BTK inhibitor-based regimens have demonstrated significant clinical activities in MCL, with emerging evidence supporting moving rationally designed novel combinations into frontline setting. A brief summary of non-chemotherapy biologic agents/combination in MCL is provided as below.

2.2.1 Evidence with lenalidomide-based regimens

In MCL-001 and MCL-002 studies for relapsed / refractory disease, single agent lenalidomide given at 25 mg on days 1-21 every 28 days showed ORR of 28%-40%, CR 5-8% and DOR over 16 months^{3,8}. The most common grade 3-4 adverse events associated with single agent lenalidomide included neutropenia (43-44%), thrombocytopenia (18-28%), and anaemia (8-11%). The addition of rituximab, given at 375 mg/m² weekly during cycle 1, to 20 mg lenalidomide, was safely tolerated and augmented activity in relapsed patients with ORR 53%, CR 31%, median PFS 14 months, and DOR 18 months⁹. When evaluated in 38 patients with previously untreated MCL, the combination of lenalidomide plus rituximab given as induction and maintenance therapy was highly effective and produced an ORR of 92% and 64% CR in evaluable patients. The median DOR and PFS was not reached after a median follow-up of 30 months. Treatment was well tolerated, with the most common grade 3-4 adverse events included neutropenia (50%), rash

(29%), thrombocytopenia (13%), tumor flare (11%), anemia (11%) and fatigue (8%). A response to treatment was associated with improvement in quality of life as measured by quality-of-life instrument⁶. Exploratory analyses were performed in some of these studies to evaluate predictive biomarkers for response and survival. The proliferation index Ki-67 was significantly associated with lower CR rate, DOR and survival in MCL-001 study¹⁰. The impact of SOX11 and TP53 expression and *IGHV* gene mutational status have not been reported in lenalidomide-based treatment.

2.2.2 Evidence with 1st generation BTK inhibitor ibrutinib-based regimens

Single agent Ibrutinib, given at a daily dose of 560 mg, demonstrated an ORR of 68% with 21% CR and a median DOR of 17.5 months in an international phase 2 study including 111 patients with relapsed or refractory MCL⁴. In a subsequent long-term follow-up study, the median treatment duration was reported at 8.3 months with 46% of patients treated for >12 months and 22% treated for ≥ 2 years. The 24-month PFS and OS rates were 31% and 47%¹¹. When given in combination with rituximab which was administered weekly x 4 during cycle 1, then on day 1 of cycles 3-8, and thereafter once every other cycle up to 2 years to 50 relapsed MCL patients, the ORR was 88% with CR at 44%¹². Treatment was well tolerated and only 10% discontinued treatment due to AEs. Ki-67 expression levels were assessed and divided into less than 50% (37 patients) and 50% or more (12 patients). Patients in the Ki-67 <50% group achieved 100% ORR with median DOR, PFS and OS not reached. Patients in the Ki-67 ≥50% group were significantly associated with worse treatment outcome, suggesting that Ki-67 might serve as a predictive biomarker of treatment responses to ibrutinib and rituximab combination in MCL. Based on data in R/R setting, an ongoing phase II single-center clinical trial at MDACC has evaluated a chemotherapy-free phase of ibrutinib-rituximab (IR) treatment (Part 1) until best response¹³, followed by a shortened intense chemo-immunotherapy course of R-hyperCVAD alternating with high-dose methotrexate-araC (Part 2) among newly diagnosed MCL patients of ≤65 years. Ibrutinib was dosed at 560 mg orally, daily, continuously. Rituximab was dosed at 375 mg/m² IV weekly x 4 during cycle 1 (28 days cycle), then day 1 of cycles 3-12. In 50 evaluable patients, overall response rate (ORR) to chemotherapy-free therapy alone was 100%, with CR in 80% (40) and PR in 20% (10). The most common grade 1-2 non-heme AEs were fatigue (50), diarrhea (28), rash (29), myalgia (41), oral mucositis (52), peripheral neuropathy (19), nausea (25), blurred vision (19), edema (23), constipation (18), dry eyes (18), and dizziness (22). Grade 3 non-heme AEs included fatigue (4), nausea (2), infection (3) and dyspnea (2). Grade 3-4 heme AEs included lymphocytosis (22), thrombocytopenia (13) and leukopenia (15). MRD status was not reported in these studies.

2.2.3 Evidence with the next-generation BTK inhibitor Acalabrutinib

Acalabrutinib (also known as ACP-196 and/or Calquence®) is a selective, irreversible small molecule inhibitor of BTK currently under clinical investigation. Acalabrutinib is an investigational product. Calquence® has been approved in the United States and other markets for the treatment of adult patients with mantle cell lymphoma (MCL) who have received at least one prior therapy, chronic lymphocytic leukemia (CLL), and small lymphocytic lymphoma (SLL). A detailed description of the chemistry, pharmacology, mechanism of action, efficacy, and safety of acalabrutinib is provided in the Investigator Brochure. The Phase 2 ACE-LY-004 study assessed

acalabrutinib monotherapy in R/R MCL pts. 124 pts were treated with acalabrutinib at 100 mg BID until POD. Investigator-assessed ORR was 81% with 40% CR. The 12-mo PFS and OS rates were 67% (95% CI, 58%-75%) and 87%, respectively ¹⁴. The most frequent AEs ($\geq 20\%$) were Grade 1/2 and included headache (38%), diarrhea (31%), fatigue (27%) and myalgia (21%). Grade 3/4 AEs ($\geq 5\%$) included neutropenia (10%), anemia (9%) and pneumonia (5%). There were no cases of atrial fibrillation. Treatment discontinuation rate due to AEs was only 6%. Importantly, acalabrutinib has not been associated with the cutaneous toxicity reported in trials with ibrutinib.

2.2.4 Data with Triple combination

The Nordic lymphoma group reported the triple combination therapy of ibrutinib-lenalidomide-rituximab (ILR) in 50 R/R MCL ¹⁵. During induction, lenalidomide was given 15 mg po daily, days 1-21, ibrutinib 560 mg po days 1-28, rituximab 375 mg/m² iv day 1 in cycle 1, then 1400 mg sc (or 375 mg/m² iv) days 8, 15 and 22 in cycle 1, then day 1 in cycles 3, 5, 7, 9 and 11. During maintenance phase, responding patients continued with ibrutinib 560 mg po days 1-56 and rituximab sc 1400mg day 1 of each cycle until progression. The most common grade 3-4 adverse events were neutropenia (38%), infections (22%), and rash (14%). In evaluable patients, ORR was 83% with CR at 41% and PR at 41%. Median duration of response and PFS has not been reached. Of the 13 patients evaluable for MRD at 6 months, 7/12 patients have achieved molecular remission in blood and 7/13 in bone marrow. Interestingly, the outcomes of patients with mutant TP53 was comparable to patients with wildtype TP53, suggesting that the triple combination might overcome the poor prognosis associated with TP53 mutations.

The ILR triple combination has also been evaluated in frontline FL and R/R DLBCL studies. The Alliance A051103 trial evaluated the combination of lenalidomide, rituximab, and ibrutinib in patients with previously untreated follicular lymphoma ¹⁶. Despite a high response rate, the activity of the regimen was challenged by poor tolerability related primarily to cutaneous toxicity (grade 3 rash at 36%). In R/R DLBCL, the ILR combination of ibrutinib 560 mg once daily, rituximab 375 mg/m² on day one for six cycles and escalating doses of lenalidomide was evaluated in a phase 1b study ¹⁷. Preliminary data showed promising activity for patients with the non-GCB subtype. The most common grade 3-4 adverse events included neutropenia (33%), maculopapular rash (15%), and anemia (11%). Phase 2 portion of the global study is actively accruing at the dose level of lenalidomide 20 mg daily, days 1-21, ibrutinib 560 mg daily, and rituximab monthly x 6.

Taken together, these data suggest activity and feasibility of combining BTK inhibitor with immunomodulatory agent lenalidomide in MCL, but also suggest that a second-generation BTK inhibitor with less cutaneous toxicity, such as acalabrutinib, would be an optimal choice in the front-line setting.

2.3 ALR Study Rationale

There is no standard, one-size-fits-all induction treatment for patients with mantle cell lymphoma. Initial treatment for MCL varies but usually includes chemoimmunotherapy and often involves intensive approaches, such as high-dose chemotherapy and hematopoietic-cell transplantation. Treatment selection is influenced by age, coexisting conditions, and individual preferences.

Optimal treatment of patients with MCL, who are frequently older (median age, 65 years) and unsuitable candidates for intensive regimens, remains a clinical challenge.

Lenalidomide is a second-generation immunomodulatory compound that has pleiotropic antitumor effects, including stimulation of T-cell and natural killer (NK)–cell expansion, inhibition of tumor-associated angiogenesis and lymphangiogenesis and induction of lymphoma cell apoptosis through the down-regulation of cyclin D1 ¹⁸. When combined with rituximab in vitro, lenalidomide augments antibody-dependent cell-mediated cytotoxicity by enhancing apoptosis and activation of NK-cell–mediated cytotoxicity and has been shown to overcome rituximab resistance in patients with lymphoma. In frontline setting, phase 2 data from Weill Cornell Medicine (WCM) have shown that the combination of lenalidomide plus rituximab is active and well tolerated with an ORR of 92% and a complete response (CR) rate of 61% in 36 evaluable patients ⁶. The 4-year PFS of 70% is particularly notable relative to historical data reported on patients receiving outpatient-based chemotherapy regimens, where median progression-free survival ranged from 16.6 to 35.4 months. There remains room for improvement in efficacy, tolerability and better-defined treatment duration.

BCR signaling is necessary to sustain the viability of B cell malignancies via constitutive activation of NF-κB pathway. An antigen-driven origin of mantle cell lymphoma has been suggested whereby BCR activation contributes to proliferative signature of MCL lymphomagenesis ¹⁹. BTK inhibitors provide therapeutic activity by blocking chronic BCR signaling leading to a decrease in NF-κB activity. Lenalidomide downmodulates IRF4, leading to an increase in IFNβ secretion and a decrease in NF-κB activity ²⁰. Combining BTK inhibitor and lenalidomide therefore appears to target key pathways in MCL which may increase therapeutic synergy and reduce overall resistance development. Additionally, combining acalabrutinib with lenalidomide + R may have theoretic advantage over ibrutinib with lenalidomide + R, given minimal impact of acalabrutinib on activation and expansion of NK/T cells compared to ibrutinib ²¹, which potentially preserves immunomodulatory amplification of lenalidomide on rituximab-induced ADCC.

The feasibility of the triple combination of BTK inhibitor + lenalidomide + rituximab in MCL has been demonstrated by the Nordic PHILEMON study which uses lenalidomide at 15 mg po daily, days 1-21, Ibrutinib 560 mg po days 1-28, and standard dose rituximab ¹⁵. Furthermore, the triple combination was experimented in a phase 1 FL frontline study and a phase I/II R/R DLBCL study. Phase 2 recommended dose was lenalidomide at 20 mg daily, days 1-21, and ibrutinib at 560 mg daily in 28-day cycle for both studies ¹⁶. Given the generally similar and well-tolerated profile of acalabrutinib and ibrutinib, we expect similar safety profile with the acalabrutinib, lenalidomide and rituximab combination in frontline MCL treatment. Because relapsed/refractory MCL has been associated with poor outcomes, every study to evaluate lenalidomide or BTK inhibitors to date, including the Nordic PHILEMON study, treatment has continued until disease progression.

Based on the relatively high clinical CR rate with frontline R2 regimen (CR 60%), and frontline IR regimen (CR 80%), we hypothesize that addition of BTK inhibitor acalabrutinib to R2 regimen would further synergize clinical activity of either agent and improve MRD negative CR rate from 60% to a target rate of 80%. The improvement in MRD CR rate would facilitate

response-adapted treatment algorithm during maintenance phase to allow for oral-drug free period to minimize AEs associated with chronic therapy. We therefore propose a single-arm phase 2 study to evaluate the preliminary evidence of efficacy and safety of the combination of acalabrutinib, lenalidomide and rituximab (ALR) in previously untreated mantle cell lymphoma. The study includes an induction phase consisting of 12 cycles of ALR. Subjects that respond to treatment will be eligible to enter a maintenance phase which will continue until disease progression, unacceptable toxicity, or voluntary withdrawal. A lead-in cohort of 6 subjects will serve as safety run-in.

2.4 Correlative Studies Background

The MRD evaluation has emerged as an attractive and highly sensitive tool for assessing the response to treatment in MCL ²². Almost all patients with MCL present with PCR-detectable dissemination to PB or BM, and MRD assessment by RQ-PCR is feasible in about 85% of advanced-stage MCL. MRD response is a strong prognostic and predictive marker for subsequent clinical outcome, indicating that early MRD eradication should be a therapeutic goal in the treatment of MCL. It is therefore of major interest to elucidate the MRD response to novel treatment to select new strategies for further investigation. LymphoTrack–Miseq platform and customized algorithm will be applied to identify lymphoma-specific rearranged immunoglobulin gene region (VDJ) in pre-treatment tissue sample(s) and to detect MRD in posttreatment PB samples.

It is of clinical utility to pursue novel biomarkers and additional means of monitoring for MRD. It has been previously reported that cell-free circulating tumor DNA follows distinct kinetic patterns of clearance from plasma in response to treatment. Development of detectable circulating tumor DNA during surveillance identified a subset of patients at elevated risk of relapse months prior to clinically evident disease ²³. DNA will be quantified in our subjects during maintenance treatment. We will also explore associations of MRD status with genomic composition of MCL and immune microenvironment during treatment as predictive biomarkers for treatment sensitivity or resistance, with the following correlative study objectives.

- To analyze kinetics of changes of peripheral blood cell-free tumor DNA (cfDNA) in the plasma following study regimen and to evaluate cfDNA in the context of response status.
- To correlate NGS mutational profile with response to treatment of the following genes: ATM, CCND1, TP53, KMT2D, NOTCH1, NOTCH2, WHSC1 and BIRC3.
- To evaluate the change in immune cells in peripheral blood, including T and NK cell subpopulations and the MDSC subset in response to treatment.
- To evaluate the plasma cytokine profile in response to treatment.

2.5 ALO Study Expansion Rationale

Obinutuzumab is a type II, glyco-engineered, humanized anti-CD20 monoclonal antibody, which was superior to rituximab in MCL xenograft models. In the phase 2 GAUGUIN study, single agent obinutuzumab demonstrated clinical activity in patients with R/R MCL including those with

rituximab-refractory disease ¹. A number of frontline phase 2 trials which recruit older MCL patients are assessing the efficacy of bendamustine plus obinutuzumab (BO) combinations. They include the phase 2 single-arm multicenter study (NCT03311126) with BO chemoimmunotherapy induction followed by consolidation and maintenance with obinutuzumab, and the phase 2 trial with the triple combination induction therapy of bendamustine, obinutuzumab and venetoclax (NCT03872180). Obinutuzumab is also being evaluated with the chemo-free combination of ibrutinib plus venetoclax in a phase 1/2 study (OAsIs, NCT02558816). The study consists of a step-wise enrollment: step A with obinutuzumab plus ibrutinib combination in R/R MCL, step B with triple combination in R/R MCL, and step C with the triplet in treatment-naïve patients ². Patients in step C were treated with Obinutuzumab at 1000mg IV on C1D1, 8, 15, C2-6 D1 and every 2 months for up to 2 years. Preliminary data on 15 treatment-naïve patients showed ORR of 100% when assessed at end of cycle 2 treatment.

The combination of obinutuzumab with lenalidomide (LO) has demonstrated favorable safety and efficacy in patients with indolent B-cell NHL including follicular lymphoma. The phase 1b GALEN study established that patients with R/R FL could safely tolerate obinutuzumab 1000 mg IV administered on days 8, 15, and 22 of cycle 1 and on day 1 of cycles 2-6, in combination with 20 mg lenalidomide given on days 1 to 21 of a 28-day cycle. The LO combination was well tolerated and effective, providing ORR of 64% ³. In the MD Anderson phase 1/2 study with LO for relapsed indolent B-cell NHL, 66 patients received Len at 20 mg given on days 1 to 21 of a 28-day cycle, plus obinutuzumab (1000mg) IV on days 1, 8, and 15 of cycle 1 and day 1 of cycles 2-6, followed by maintenance every 2 months for a maximum of 30 months on study. The ORR for all pts was 98% with CR at 72% ⁴. When given in the frontline setting for 90 patients with untreated high burden follicular lymphoma, the same MD Anderson LO treatment schedule achieved ORR of 98% with CR at 92%. The treatment was well tolerated with manageable toxicity profile, including grade 3/4 neutropenia at 16%, rash at 10% and lung infection at 4% and neutropenic fever at 1% ⁵.

Given the safety and efficacy data of obinutuzumab combinations in mantle cell lymphoma, and the impressive efficacy of obinutuzumab plus lenalidomide combination in indolent lymphoma, we hypothesize that the obinutuzumab-based triple combination of acalabrutinib-lenalidomide-obinutuzumab (ALO) has the potential to improve efficacy while maintaining safety and tolerability compared to the ALR combination in the frontline setting. We propose to add a feasibility cohort of 10 MCL patients to assess safety and preliminary efficacy with the ALO regimen. We recommend commencing the accrual of the ALO cohort following enrollment completion of the ALR cohort.

3. SUBJECT SELECTION

3.1 Study Population

Adults with previously untreated mantle cell lymphoma who meet the inclusion and exclusion criteria will be screened for eligibility. Screening procedures are outlined in Section 5, Schedule of Evaluations and unless otherwise specified, must take place within 28 days prior to initiation of

therapy. Approximately 28 subjects with previous untreated mantle cell lymphoma will be screened for enrollment and must meet the eligibility criteria below.

3.2 Inclusion Criteria

- Histologically confirmed diagnosis of mantle cell lymphoma
- Age \geq 18 years
- No prior systemic therapy for lymphoma
- Measurable disease defined by a tumor mass \geq 1.5 cm in one dimension and measurable in two dimensions; patients with measurable spleen disease are allowed
- Treatment should be indicated according to the treating physician
- ECOG performance status \leq 2
- Required initial laboratory parameters:
 - Absolute neutrophil count (ANC) \geq 1000 cells/mm³
 - Platelet count \geq 75,000 cells/mm³
 - Calculated creatinine clearance \geq 30 ml/min by Cockcroft-Gault formula
 - Total bilirubin \leq 1.5 x ULN
 - AST/SGOT and ALT/SGPT \leq 3.0 x ULN
- Able to take aspirin (81 or 325 mg) daily as prophylactic anticoagulation (patients intolerant to ASA may use low molecular weight heparin).
- All subjects must be registered into the mandatory Revlimid REMS® program, and be willing and able to comply with the requirements of Revlimid REMS®.
- Patients of reproductive potential agree to use highly effective birth control throughout their participation in this study, for at least 28 days following study termination, and for 160 days for males and 12 months for females after the last dose of rituximab, 180 days for males and 18 months for females after the last dose of obinutuzumab.
- Females of reproductive potential must adhere to the scheduled pregnancy testing as required in the Revlimid REMS® program. Females of childbearing potential (FCBP) must have a negative serum or urine pregnancy test with a sensitivity of at least 50 mIU/mL within 10 – 14 days and again within 24 hours prior to prescribing lenalidomide for Cycle 1 (prescriptions must be filled within 7 days). FCBP must either commit to continued abstinence from heterosexual intercourse or begin one highly effective method and one additional effective method AT THE SAME TIME, at least 28 days before and continue for at least 28 days after the last dose of lenalidomide (or 2 days after the last dose of acalabrutinib, whichever is longer). FCBP must also agree to ongoing pregnancy testing. Men must agree to use a latex condom during sexual activity with a FCBP through one week post last dose even if they have had a successful vasectomy. Men must also agree to refrain from sperm donation during the same timeframe. See Appendix I: Risks of Fetal Exposure, Pregnancy Testing Guidelines and Highly Effective Birth Control Methods.

- Understand and voluntarily sign an ICF prior to any study related assessments and procedures are conducted.
- Able to adhere to the study visit schedule and other protocol requirements.

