- Patients of reproductive potential agree to use highly effective birth control throughout their participation in this study, for at least 28 days following study termination, and for 160 days for males and 12 months for females after the last dose of rituximab, 180 days for males and 18 months for females after the last dose of obinutuzumab.
- Females of reproductive potential must adhere to the scheduled pregnancy testing as required in the Revlimid REMS® program. Females of childbearing potential (FCBP) must have a negative serum or urine pregnancy test with a sensitivity of at least 50 mIU/mL within 10 – 14 days and again within 24 hours prior to prescribing lenalidomide for Cycle 1 (prescriptions must be filled within 7 days). FCBP must either commit to continued abstinence from heterosexual intercourse or begin one highly effective method and one additional effective method AT THE SAME TIME, at least 28 days before and continue for at least 28 days after the last dose of lenalidomide (or 2 days after the last dose of acalabrutinib, whichever is longer). FCBP must also agree to ongoing pregnancy testing. Men must agree to use a latex condom during sexual activity with a FCBP through one week post last dose even if they have had a successful vasectomy. Men must also agree to refrain from sperm donation during the same timeframe. See Appendix: Risks of Fetal Exposure, Pregnancy Testing Guidelines and Highly Effective Birth Control Methods.
- Understand and voluntarily sign an ICF prior to any study related assessments and procedures are conducted.
- Able to adhere to the study visit schedule and other protocol requirements.

Exclusion criteria:

- Patients with blastoid histology
- Patients with known or suspected CNS involvement
- Viral infection with HIV or hepatitis type B or C. Seropositive HBV patients are eligible if they are negative for HBV DNA by PCR and receive concomitant antiviral therapy during treatment and for additional six months after coming off study.
- Prior history of malignancies other than MCL unless the patient has been disease free for \geq 5 years from the signing of the ICF. Exceptions include basal cell carcinoma or squamous cell carcinoma of the skin; carcinoma in situ of cervix; carcinoma in situ of breast, or localized prostate cancer

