Implants and levonorgestrel-releasing intrauterine systems are associated with an increased risk of infection at the time of insertion and irregular vaginal bleeding. Prophylactic antibiotics should be considered particularly in patients with neutropenia.

Pregnancy testing

Medically supervised pregnancy tests with a minimum sensitivity of 50 mIU/mL must be performed for females of childbearing potential, including females of childbearing potential who commit to complete abstinence, as outlined below.

Before starting lenalidomide

Female Patients:

FCCP must have two negative pregnancy tests (sensitivity of at least 50 mIU/mL) prior to prescribing lenalidomide. The first pregnancy test must be performed within 10-14 days prior to prescribing lenalidomide and the second pregnancy test must be performed within 24 hours prior to prescribing lenalidomide. The patient may not receive lenalidomide until the Investigator has verified that the results of these pregnancy tests are negative.

Male Patients:

Must agree to practice complete abstinence or agree to use a condom during sexual contact with pregnant females or females of childbearing potential throughout the entire duration of lenalidomide treatment, during dose interruptions and for at least 28 days following lenalidomide discontinuation, even if he has undergone a successful vasectomy.

During study participation and for 28 days following lenalidomide discontinuation

Female Patients:

- FCBP with regular or no menstrual cycles must agree to have pregnancy tests weekly for the first 28 days of lenalidomide treatment, including dose interruptions and then every 28 days throughout the remaining duration of lenalidomide treatment, including dose interruptions, at lenalidomide discontinuation, and at Day 28 following lenalidomide discontinuation. If menstrual cycles are irregular, the pregnancy testing must occur weekly for the first 28 days of lenalidomide treatment, including dose interruptions, and then every 14 days throughout the remaining duration of lenalidomide treatment, including dose interruptions, at lenalidomide discontinuation, and at Day 14 and Day 28 following lenalidomide discontinuation.
- At each visit, the Investigator must confirm with the FCBP that she is continuing to use two reliable methods of birth control at each visit during the time that birth control is required.

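### Section 3.2 and the Protocol Summary end men's condom and sperm-donation restrictions one week after an unspecified last dose, while Appendix I runs to at least 28 days after lenalidomide

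*Combined protocol and SAP*

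**What the plan says.** **Eligibility text.** Section 3.2 and the Protocol Summary carry the same wording: "Men must agree to use a latex condom during sexual activity with a FCBP through one week post last dose". The condom duty holds "through one week post last dose even if they have had a successful vasectomy". The next sentence adds: "Men must also agree to refrain from sperm donation during the same timeframe". Neither place says which drug's last dose is meant. The women's rule in the same bullet does name its drugs. It runs to at least 28 days after lenalidomide, with the alternative "or 2 days after the last dose of acalabrutinib, whichever is longer".

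**Appendix I.** Under the heading for the period before lenalidomide starts, male patients face this condition: "Must agree to practice complete abstinence or agree to use a condom during sexual contact with pregnant females or females of childbearing potential". It lasts through treatment and dose interruptions, and then "for at least 28 days following lenalidomide discontinuation, even if he has undergone a successful vasectomy". The same duty is repeated for the period of study participation. A separate list of precautions says men should not donate semen or sperm during therapy or for at least 28 days after lenalidomide.

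**Section 12.2.2 (Male Subjects).** Men are advised to use abstinence or condoms during treatment and for 28 days after stopping it. Sperm donation is not mentioned.

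**Antibody rule.** An earlier bullet of Section 3.2 requires patients of reproductive potential to use highly effective birth control "for 160 days for males and 12 months for females after the last dose of rituximab, 180 days for males". The 180-day figure belongs to obinutuzumab, for which the women's period is 18 months.

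**The concern.** An eligibility criterion and the appendix it refers to give different lengths for the same precaution. Registration under Section 4 rests on an eligibility checklist signed by the investigator and a research nurse. Anyone checking that list against Section 3.2 meets one week, not 28 days.

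The precaution concerns fetal exposure. Appendix I explains the condom duty after vasectomy by traces of lenalidomide in semen, and says a teratogenic effect in humans cannot be ruled out. Because the last dose is not tied to a drug, the length of the eligibility rule also depends on how each site reads it. Acalabrutinib, lenalidomide and the antibody need not end on the same day.

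**Working it through.** The plan gives no figure of its own to reproduce. The check compares the two periods under each reading of the last dose.

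**Inputs**
- Eligibility rule: 7 days after the last dose (Section 3.2, Protocol Summary).
- Appendix I rule: at least 28 days after lenalidomide.
- Lenalidomide is given on days 1 to 21 of a 28-day cycle, and acalabrutinib continuously (Sections 5.1.1, 5.1.2).
- In maintenance the antibody is given on day 1 of even-numbered cycles (Section 5.1.2). It continues when the oral drugs stop after cycle 24 for MRD-negative CR (Section 5.1).
- All drugs can also stop together, for example on leaving the study after three years (Section 5.5).

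**Formulas**
- Study day = (cycle − 1) × 28 + day.
- d = days from the last lenalidomide dose to the last dose as read.
- Current cover after lenalidomide = d + 7.
- Shortfall = max(0, 28 − (d + 7)).
- Cover under the proposed wording = max(28, d + 7).

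**Study days**
- Cycle 24 day 21 = 23 × 28 + 21 = 665.
- Cycle 24 day 28 = 23 × 28 + 28 = 672, so d = 672 − 665 = 7.
- Cycle 26 day 1 = 25 × 28 + 1 = 701, so d = 701 − 665 = 36.

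| Reading of the last dose | d | Current cover | Shortfall | Proposed cover |
|---|---|---|---|---|
| Lenalidomide, or all drugs stop together | 0 | 7 | 21 | 28 |
| Acalabrutinib on day 28 is the last dose | 7 | 14 | 14 | 28 |
| Any study drug, antibody continues to at least cycle 26 day 1 | 36 | 43 | 0 | 43 |

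The 43 days are a floor. Each later antibody infusion pushes the end date further out under that reading. A repair tied to lenalidomide alone would give 28 days in the third row, which is 43 − 28 = 15 days less than the current text allows.

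**Does the antibody rule fill the gap?** It asks for highly effective birth control. Appendix I lists the male condom only as an additional effective method, and its examples of highly effective methods include an intrauterine device. The rule can therefore be met without a condom. It is silent on sperm donation and on condom use after vasectomy. It also gives nothing where the partner is already pregnant, a case Appendix I names. The 160 and 180 days measure a different obligation.

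**Proposed wording against Section 12.2.2.** Counted from the last lenalidomide dose, advice of 28 days after stopping treatment gives 28, 7 + 28 = 35, and 36 + 28 = 64 days in the three rows. The last figure assumes the antibody counts as treatment. The proposed rule gives 28, 28 and 43. It therefore sets a minimum and should not displace that advice.

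**The case against.** The strongest reply is that the periods are compatible and the longer one already binds. A man who follows Appendix I for 28 days after lenalidomide also meets one week after lenalidomide. Nothing in Section 3.2 permits him to stop before Appendix I allows. Section 3.2 points to the appendix, the Appendix I condition is itself an agreement made before treatment, Revlimid REMS compliance is mandatory, and patients must meet the criterion "Able to adhere to the study visit schedule and other protocol requirements".

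The pharmacology points the same way. Section 7.2.3 gives a plasma half-life of 2.8 to 6.1 hours without accumulation. Seven days is 168 hours, or 168 / 6.1 = 27.5 half-lives at the slow end.

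Most of this stands, and it is why the point is minor. It lowers the practical risk but does not reconcile the texts. The half-life is a plasma figure. The documents give no value for semen, or for renal impairment, although Section 3.2 admits creatinine clearance down to 30 ml/min. The male REMS period is not stated either.

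Two stronger readings are tempting. A reader might infer that men were told one week. The consent pages and REMS materials are not in the documents, so this cannot be checked. A reader might also infer that the shortfall is an established fetal exposure. The documents show a difference in stated duration, not in drug exposure.

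**Conclusion.** The inconsistency is real and lies in current text. The eligibility criterion is shorter than Appendix I by 21 or 14 days on two readings of the last dose and not shorter on the third. These figures assume dosing on the protocol schedule.

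It would go too far to call the gap a uniform 21 days, because the unnamed drug leaves the period open. It would also be wrong to treat the antibody rule as limiting the gap to vasectomised men. A fertile man can meet that rule without a condom, and sperm donation and pregnant partners lie outside it.

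No endpoint, sample size or analysis is touched. Severity: minor, a correction of safety wording.

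**What to change.** In Section 3.2 and the Protocol Summary, replace the two sentences on men with a single rule along these lines:

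> Men must agree to abstain or use a condom with any partner who is pregnant or of childbearing potential, including after vasectomy, and not to donate sperm. This applies during treatment and dose interruptions, and until the later of two dates: at least 28 days after the last lenalidomide dose, or one week after the last dose of any study drug (see Appendix I).

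This adds the pregnant partner and the abstinence option that Appendix I already contains. It never shortens the present cover.

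In the Appendix I precautions, change *should not* to *must not* for semen and sperm donation, so that the duty has the same force in both places. Leave the advice in Section 12.2.2 and the 160- and 180-day antibody rule in force.

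The cost is a short protocol amendment, with supporter review before IRB submission (Section 10.2). It adds no visits or tests. The eligibility checklist and consent form should be checked against the new wording.
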